PUSH PLUS PROTEIN PILOT STUDY FOR HIP FRACTURE PATIENTS
PROTOCOL (Version 3.0)

Summary of Modifications to Protocol Version 2.0 for Version 3.0

Version (date)	Section	Brief Summary of Modification
9-5-2018	10.1 and 10.2	We removed the Biodex ankle plantarflexion-dorsiflexion measurement from the baseline and 16-week follow-up assessments. We will test Biodex knee flexion/extension only, which is the best representative marker for torque/ power production and importantly related to gait and mobility function. The Biodex ankle test is less reliable and the knee test a better performance predictor. When investigators looked at data from the CAP-MP companion study, they learned that many in this functionally very challenged cohort could not achieve the 60 deg/sec needed to perform the ankle test; thus, the torque/power was not calculated, as there was more missing data for the Biodex ankle test than for the Biodex knee test which was more complete. The ankle test for the selected contraction velocity is more difficult for many in this study population to achieve in order to capture valid measurement. Therefore, experts in the Department of Physical Therapy and Rehabilitation Science (PTRS) suggest using the Biodex knee test only for the current pilot study because it more accurately represents the entire subject cohort being tested. Participants will be able to correctly perform the knee test which was not true for the ankle test in the companion study.
	10.1 and 10.2	We added the Four-Square Step Test (FSST) to be done at the baseline and 16-week follow-up visits as a dynamic balance assessment.

Summary of Modifications to Protocol Version 1.0 for Version 2.0

Version (date)	Section	Brief Summary of Modification
7-24-2018	All sections	Changed study clinician to study physician
	12.5 and Figures 5b-d	Modified procedures for reportable adverse events to coincide with reporting procedures outlined by NIA and the Pepper Center OAIC.
	7.5	Modified recruitment procedures to describe how patients will be contacted after discharge from the hospital and how potential participants who contact the study office will undergo a brief pre-screening to assess eligibility.
	17	Modified the publication policy to state that publications will be overseen by study leadership and added a note that final papers using CAP or CAP-MP data may need to be reviewed by the CAP PASC.

PUSH Plus Protein Pilot Study for Hip Fracture Patients

Principal Investigator:

[name]

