7.1.1 Required Baseline Data

Certain components of the baseline assessment must be completed by all participants in the pilot study in order to make useful comparisons to data from participants in CAP and CAP-MP and to have enough power to achieve primary and secondary research aims. Participants who perform the required components (identified in Section 10: Study Procedures) no later than 26 weeks after hospital admission for the hip fracture will be said to have complete baseline data and thus be eligible to receive the PUSH Plus Protein intervention.

Figure 2. Algorithm for Screening

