7.3 Exclusion Criteria

4. Logistical impediments to participation
 - 4.1 Does not live within reasonable distance of the clinical center
 - 4.2 Participant plans to move out of area or otherwise be unavailable during the 16-week intervention period
 - 4.3 Participation in another clinical trial
 - 4.4 Not English speaking
 - 4.5 Baseline testing not completed by 26 weeks post admission for hip fracture
 - 4.6 Final sign off from study physician and/or principal investigator is incomplete
 - 4.7 Incomplete baseline data
 - 4.8 Unable to contact participant
 - 4.9 Participant is unable to provide her/his own informed consent
 - 4.10 Participant refuses the study
5. Medical impediments to participation or low potential for benefit from interventions
 - 5.1 Calculated creatinine clearance < 15 ml/min
 - 5.2 Serum albumin < 2.5 g/dl

- 5.3. End stage renal disease on dialysis (CKD stage 5 or 6)
- 5.4. Lower extremity amputation
- 5.5. Cognitive impairment (3MS score <73)
- 5.6. Severely diminished lower extremity sensation or ulceration
- 5.7. Participant walks less than four meters in 40 seconds (<0.1 m/sec)
- 5.8. Not community-residing (e.g., resident of a skilled nursing facility) at time of baseline testing
- 5.9. Receiving PT for the hip fracture in the hospital or in an inpatient rehabilitation facility at time of baseline testing

- 6. Medical contra-indications for exercise
 - 6.1. Hemoglobin < 9 g/dl
 - 6.2. Symptoms of angina pectoris
 - 6.3. Recent myocardial infarction
 - 6.4. Uncompensated congestive heart failure
 - 6.5. Chest pain or shortness of breath (including from severe chronic obstructive pulmonary disease)
 - 6.6. Uncontrolled hypertension
 - 6.7. Not fully weight-bearing on fractured leg or non-fractured leg at time of baseline testing
 - 6.8. Study physician thinks participant is not a good candidate for study (e.g., not likely to survive study period)
 - 6.9. Development of chest pain or substantial shortness of breath or ambulating with severe pain during baseline SMWT

- 7. Medical contra-indications for whey protein supplement
 - 7.1. Chronic kidney disease (CKD stage 4)
 - 7.2. Severe liver disease (e.g., hepatitis, fatty liver disease, cirrhosis)
 - 7.3. Hemoglobin A1c level > 10%
 - 7.4. Known dairy allergy
 - 7.5. Known celiac disease
 - 7.6. Known history of severe, life-threatening peanut or shellfish allergy
 - 7.7. Calculated creatinine clearance 15-29 ml/min

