10.1 Baseline Assessments

The baseline assessments will be performed immediately following screening for phase 3 criteria.

Certain components of the baseline assessment are required by all participants in the pilot study in order to make useful comparisons to data from participants in CAP and CAP-MP and to have enough power to achieve primary and secondary research aims. Other assessments at the baseline visit will allow comparisons for other outcome measures. Participants who perform the required components (marked with a pound sign (#) in the list below) will be eligible to receive the PUSH Plus Protein intervention. All baseline data collection must be completed within 14 days of the SMWT.

The items with an asterisk (*) are collected as part of phase 3 screening:

- Baseline Anthropometry #
- Demographics and Blood Draw Information # *
- Modified Mini-Mental State Examination # *
- Six-Minute Walk Test # *
- Baseline Interview #
- Short Physical Performance Battery #
- SF-36 Health Survey #
- Pepper Assessment Tool for Disability #
- Mini Nutritional Assessment-Short Form #
- Trail Making Test (Trails A and B)
- Blood draw (for serologic and genetic tests)
- Reportable Adverse Events
- CT scan of thigh #
- DXA scan of whole body #
- DXA scan of hip
- GAITrite
- Four-Square Step Test
- Bidex strength testing (knee flexion/extension)

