10.4 Timing of Study Procedures

The target date for completion of the pre-baseline testing (i.e., screening) assessments will be anchored to the date of admission to the hospital for hip fracture. The target date for completion of all other assessments will be anchored to the date on which all baseline testing is completed (see Table 1).

Note: In cases where the participant performs all required baseline measures and then performs additional baseline measures, the date on which baseline testing is completed is defined as the date on which the participant performed the last assessment within the allowable window for baseline testing (up to 26 week post hospital admission). In cases where additional baseline measures have been scheduled but cannot be completed within the allowable window for baseline testing, (e.g., scheduling conflict, not safe), the date on which baseline testing completed is defined as the date on which staff establishes definitively that no additional baseline measures can or will be attempted.

Table 1. Timing of Study Procedures

PROCEDURE	TARGET DATE	ALLOWABLE INTERVAL
Phase 3 screening	As early as possible following admission	Up to 26 weeks post-admission
Baseline assessment	As early as possible following admission	Up to 26 weeks post-admission
Dietitian consult	1 week after baseline testing is completed	+1 week
First intervention visit	1 week after baseline testing is completed	+16 weeks
First telephone interview	4 weeks after baseline testing is completed	-1 week, +3 weeks
Subsequent telephone interviews	At 4-week intervals from date on which baseline testing is completed	-1 week, +3 weeks
First follow-up assessment	16 weeks after baseline testing is completed	+2 weeks
Out-of-window assessment	16 weeks after baseline testing is completed	0-16 weeks and 18-38 weeks after baseline testing is completed

At baseline, all participants will, by design, be tested at the clinical site. At the follow-up visit, we will attempt to test all participants at the clinical site. When this is not possible, we will attempt to have study staff administer the test in a non-study clinical facility or, failing that, at another non-study location or the participant's home.

Section 11: Safety Assessments

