11.1.2 Safety Considerations for Study Assessments

All study assessments will be done by certified staff who will be trained to perform the tests safely. If, during the SMWT or the SPPB a participant reports chest pain, tightness or pressure, significant shortness of breath or difficulty breathing, or feeling faint, lightheaded, or dizzy, the test will be stopped. If the participant weighs more than 400 pounds or if s/he is unable to lie supine, the whole body and hip DXA scans will not be done. Participants with prior hardware in the non-fractured hip will not have a hip DXA scan. If a participant is unable to lie supine or be left alone in a room, the thigh CT scan will not be done. Participants unable to put full weight on the fractured side or unable to stand for 30 seconds without an assistive device will not perform the GAITrite or Biodex measures. All research staff who come in contact with study participants will be CPR certified and will be trained to provide immediate care when faced with medical emergencies. Also, institutional and community emergency medical services will be activated if needed.

Table 2 describes a summary of safety alerts and the appropriate action during clinical assessments.

Table 2. Safety Alerts and Actions for Study Assessments

ALERT	ACTION
Resting blood pressure SBP > 145mm Hg or DBP > 90mm Hg	Qualified staff will inform the participant if noted on more than one occasion.
Resting blood pressure SBP > 170mm Hg or SBP < 90mm Hg or DBP > 100mm Hg or DBP < 50mm Hg	Qualified staff will encourage the participant to seek additional follow-up and/or medical evaluation. Physical performance testing will be deferred until consultation with the study physician.
Resting blood pressure or after SMWT SBP > 185mm Hg or SBP < 90mm Hg or DBP > 110mm Hg or DBP < 50mm Hg	Qualified staff will consult with the study physician and follow up as needed.
Resting pulse Rate > 120 or < 40 beats/min	Qualified staff will consult with the study physician and follow up as needed.

Table 2. Safety Alerts and Actions for Study Assessments

Chest pain, dizziness, significant shortness of breath, or severe musculoskeletal pain during the intervention or study assessment.	Qualified staff will consult with the study physician and follow up as needed.
MNA®-SF Score \leq 7 at the follow-up assessment	Qualified staff will talk to the participant and provide a referral for additional follow-up and/or medical evaluation for possible malnutrition.

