14.3 Missing Data

By design, there will be no missing data at baseline because only participants with complete baseline data will be randomized. At follow-up, scores for scales that have published rules for handling missing scale items (e.g., the CES-D and the SF-36) will be calculated using those rules. All other scales will be considered missing if any part of the scale is missing. To correct for potential selection bias from missing data, we will perform a weighted estimating equations (WEE) analysis.¹⁶⁹ This method involves two steps. First the probability of being observed (not missing) is calculated as a function of predictors of missingness. Next the relationship of treatment group to outcome is assessed using the inverse probability of being observed as a weight in the GEE model. WEEs are advantageous because a) they are consistent with the ITT principle because participants with missing data are included in the analysis through the estimated weight, and b) unlike other methods for addressing missing data, they can be performed in conjunction with marginal structural modeling by multiplying both weights together.

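### The no-missing-baseline statement in 14.3 and the SAP holds only for the # components; separately, the CAP-MP detectable difference of 0.62 SD does not match the planned b3 contrast, which gives 0.67 SD

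*Protocol*

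**What the plan says.** Protocol 14.3 and the Missing Data section of the SAP carry the same sentence: "By design, there will be no missing data at baseline because only participants with complete baseline data will be randomized". No outcome is exempted. The text then deals with missing scores at follow-up and describes a GEE weighted by the inverse probability of being observed.

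Protocol 7.1.1 defines the key term. Participants who perform the required components in time "will be said to have complete baseline data and thus be eligible to receive the PUSH Plus Protein intervention". Section 10.1 says which these are: "Participants who perform the required components (marked with a pound sign (#) in the list below) will be eligible to receive the PUSH Plus Protein" intervention. The # list includes the six-minute walk (SMWT), 3MS, SPPB, SF-36, PAT-D, MNA-SF, thigh CT and whole-body DXA. The blood draw for serology, hip DXA, GAITrite, Biodex, Trails and the Four-Square Step Test have no #.

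Section 10.4 fixes the date on which baseline testing ends "In cases where additional baseline measures have been scheduled but cannot be completed within the allowable window for baseline testing". Section 11.1.2 adds that those "unable to stand for 30 seconds without an assistive device will not perform the GAITrite or Biodex measures", and that "Participants with prior hardware in the non-fractured hip will not have a hip DXA scan".

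Protocol 14.2 and the SAP estimate the effect through b3, the group difference in change from baseline to 4 months. Section 14.4 and the SAP assume r = 0.70, two-sided alpha 0.05 and 80% power. They give 0.475 SD for 94 vs 27 (CAP) and 0.62 SD for 17 vs 27 (CAP-MP).

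**The concern.** The tests without # supply five of the six mechanistic aims in the Executive Summary: strength, gait, hip bone density, bone turnover and cytokines. Each is analysed through b3, which uses the baseline value. A participant may start treatment without that value and still be measured at 16 weeks. The plan says this cannot happen, and it does not say whether the weights count a missing baseline value as unobserved.

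The CAP-MP sample of 17 vs 27 is 90% of 19 and 30 (17.1 and 27), so it allows for loss to follow-up only. Checking that figure brings up a second matter that has nothing to do with missing baselines: it rests on a different variance formula from the CAP figure in the same section. The pilot is meant to inform the size of a definitive study, so its precision statement should match its own model.

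**Working it through.** **1. Which measures can be missing at baseline**

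| Measure (mechanistic aim) | # | Documented reason for not being done |
|---|---|---|
| Thigh CT (a), whole-body DXA | yes | If not done, baseline data are incomplete and the person is excluded (7.3, item 4.7) |
| Biodex knee (b), GAITrite (c) | no | Cannot stand 30 seconds unaided |
| Hip DXA (d) | no | Hardware in the other hip |
| Serology (e, f) | no | None specific; only the general provision in 10.4 |
| Trails, Four-Square Step Test | no | None specific; only the general provision in 10.4 |

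Two apparent reasons drop out. The weight-bearing half of the GAITrite and Biodex rule is already an exclusion (item 6.7: "Not fully weight-bearing on fractured leg or non-fractured leg at time of baseline testing"). The body-weight and supine limits for hip DXA also apply to the required whole-body scan, so they lead to exclusion. A function-related reason therefore remains only for GAITrite and Biodex. Hardware in the other hip costs hip DXA numbers at both visits.

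**2. The detectable difference, with no baseline loss**

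Inputs from 14.4: r = 0.70, two-sided alpha 0.05, 80% power. With the normal approximation, k = 1.960 + 0.842 = 2.802.

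- Change contrast (b3): k × √(2(1 − r)) × √(1/n1 + 1/n2), with √(2 × 0.30) = 0.7746
- Baseline-adjusted: k × √(1 − r²) × √(1/n1 + 1/n2), with √0.51 = 0.7141

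| Comparison | Stated | Change contrast | Baseline-adjusted |
|---|---|---|---|
| 94 vs 27 | 0.475 | **0.474** | 0.437 |
| 17 vs 27 | 0.62 | 0.672 | **0.619** |

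The CAP figure follows the first formula and the CAP-MP figure the second. Only the first fits b3. Using the t distribution does not remove the gap: at 17 vs 27 it gives 0.688 and 0.634. Nor does adding the people with a baseline value only (2 and 3), which gives 0.667 in an all-available-data GEE.

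Power at 0.62 SD: the SE of b3 is 0.7746 × 0.3096 = 0.240 SD. Then 0.62/0.240 − 1.960 ≈ 0.625, and Φ(0.625) = 0.734.

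Other correlations, change contrast at 17 vs 27:
- r = 0.78 (walking speed, 14.1): 2.802 × √0.44 × 0.3096 = 0.575
- r = 0.80 (edge of the range in 14.1): 2.802 × √0.40 × 0.3096 = 0.549
- To reach 0.62: √(2(1 − r)) = 0.62/(2.802 × 0.3096) = 0.715, so r ≈ 0.745

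**3. Illustration of baseline loss (assumed rate)**

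The documents give no rate. If 10% in each group lacked a baseline value, complete pairs (15 vs 24) would give 2.802 × 0.7746 × √(1/15 + 1/24) = 0.714 SD. An all-available-data GEE, with 2 and 3 further people seen only at each visit, would give 0.701 SD. Power at 0.62 SD would be 68% to 70%.

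**4. Illustration of bias (assumed rates and deficit)**

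Suppose the people seen only at 16 weeks score 1 SD lower. The bias in b3 is (difference in their share between groups) × 1 × (1 − r). For 20% vs 10% it is 0.10 × 0.30 = 0.03 SD. For 20% vs 0% it is 0.20 × 0.30 = 0.06 SD, a quarter of the SE (0.06/0.24).

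**The case against.** *The baseline sentence is only loose wording.* Complete baseline data is a defined term, and read with that definition 14.3 covers the primary outcome and every outcome named in 14.2. The reference to randomisation suggests text carried over from another study, and the weighting step is described generally enough to include a missing baseline. Most of this stands, and it is why the point is modest. But 14.3 and the SAP do not repeat the definition, and 14.2 applies b3 to the mechanistic factors, where the sentence is not true.

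*The 0.62 SD mismatch is a separate issue.* Correct: it exists with no missing baseline at all, and baseline loss does not explain it.

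*r = 0.70 is called conservative.* Section 14.1 reports r above 0.80 for various physiologic measures, and at 0.80 the change contrast detects 0.55 SD. So the practical shortfall may be nil for some outcomes. Still, 14.4 states 0.70 and its companion figure uses it. The 0.78 comes from walking speed in 13 people, and the documents do not assign the higher value to particular CAP-MP measures.

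*A baseline-adjusted analysis would justify 0.62.* It would, but both documents specify b3. In a non-randomised comparison the two contrasts also differ when baseline means differ.

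Some stronger readings are tempting and not supported:
- That the primary comparison is compromised. The SMWT carries #.
- That Biodex baselines will often be missing. The Version 3.0 change summary says of CAP-MP that "there was more missing data for the Biodex ankle test than for the Biodex knee test which was more complete". It gives no rate and no visit.
- That baseline loss is heavy enough for a much larger detectable difference. Beyond a small assumed rate, the answer depends on how far baseline loss overlaps with loss to follow-up, which is unknown.
- That weights should correct GAITrite and Biodex. The stand rule is deterministic: those who fail it are never tested, and no weight can represent them.

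**Conclusion.** Two corrections are warranted, and neither touches the primary result.

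First, the statement that no baseline data can be missing is true for the # components only. It is wrong as written for serology, hip DXA, GAITrite, Biodex, Trails and the Four-Square Step Test, and nobody is randomised. How much will be missing cannot be learned from the documents, which also do not say whether all 19 CAP-MP participants have each measure. Bias in b3 is probably small: 0.03 to 0.06 SD under the assumptions shown.

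Second, at the plan's own r = 0.70, alpha and sample sizes, the CAP-MP detectable difference for b3 is 0.67 SD, and power at 0.62 SD is about 73%. This applies to every outcome compared only with CAP-MP, including those with complete baselines. It rests on the normal approximation and on r = 0.70; at r of about 0.745 or more the change contrast reaches 0.62 SD.

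**What to change.** 1. In 14.3 and the SAP, say that baseline data are complete by design only for the components marked # in 10.1. Replace *randomized* with *start the intervention*. List serology, hip DXA, GAITrite, Biodex, Trails and the Four-Square Step Test as measures that may be missing at baseline.
2. In 14.4 and the SAP, restate the CAP-MP detectable difference as 0.67 SD at r = 0.70, with 0.58 at r = 0.78 and 0.55 at r = 0.80 for context. Note that it allows for loss to follow-up only and is larger where baseline values are missing. Label any illustration as an assumption, for example about 0.70 to 0.71 SD at 10%.
3. Report baseline missingness by outcome and group, including CAP-MP. Keep the all-available-data GEE, and add a paired-case sensitivity analysis for the outcomes without #. State that GAITrite and Biodex results describe those who could be tested. A baseline weight model is not needed.

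The cost is a few sentences, one table, one restated figure and a small extra analysis. The stated detectable difference becomes less favourable. No new data or visits are required.

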8.6 Scheduling Intervention Visits

There are three requirements for scheduling of intervention visits:

1. The first intervention visit should occur on Day 7 or earlier, where the last day of baseline testing = Day 0.
2. The schedule of intervention visits is anchored to the date on which baseline testing is completed regardless of when the intervention starts.
3. Intervention visits should never occur on two consecutive days, even when moving from one week to the next.

Participants who provide required baseline data are eligible to receive the intervention; however, the intervention will not begin until after the date all baseline measures are completed. Baseline data collection must be completed within 14 days of the SMWT. Week 1 will begin on the day of the first intervention visit or on Day 7 after baseline testing is complete, whichever is earlier.

Subsequent weeks will start on the same day of the week as Week 1. For example, if the participant's first intervention visit is on a Wednesday, each intervention week for that participant will extend from Wednesday to Tuesday (inclusively). Alternatively, if the first visit has not yet occurred by Day 7 and Day 7 is a Monday, then the participant's intervention weeks will extend from Monday to Sunday (inclusively).

In certain circumstances (e.g., illness, travel), the first intervention visit may be scheduled after Day 7.

Ideally participants will receive 2 visits per week for 16 weeks after complete baseline testing (32 visits total). However, missed visits in a given week can be replaced by makeup visits in subsequent weeks (not to exceed 3 visits in any given week) as long as the visits are on non-consecutive days. If the participant has not had 32 visits by the end of 16 weeks, makeup visits can be performed during the subsequent two weeks to get as close as possible to the target of 32 visits.

Section 9: Study Measures

A list of study measures is provided below. All of the measures will be interview-based or based on observations of performance or physiological assessments. No proxy data will be allowed at baseline. However, at the 16-week follow-up visit, a proxy may be contacted to provide information about the participant's walking ability. Also, the four-week phone calls to obtain information on recent health events will be conducted with a proxy when the participant is not available

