9.3.3 Activities of Daily Living (ADLs)

We will measure ADLs using the Pepper Assessment Tool for Disability (PAT-D)^{145,146} with two modifications. First, two items (walking a quarter mile and walking across a small room) were added to address perceived gaps in the original PAT-D scale. This modification is consistent with the version used in the Lifestyle Interventions and Independence for Elders study.¹⁴⁷ Second, two items (walking several blocks and lifting heavy objects) were deleted to avoid duplication with other items in the scale. The resulting 19-item scale allows examination of three subscales (basic ADL, functional limitations, and instrumental ADL).

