14.2 Secondary Objectives

A longitudinal analysis using Generalized Estimating Equations (GEEs) will be employed. A model of the form $Y(t) = a + b_1 X + b_2 t_4 + b_3 X t_4$ will be used where: $Y(t)$ is the dependent variable Y at time t (which is 0 or 4 months post baseline testing); a is the intercept; X is an indicator variable for treatment group (PUSH vs PUSH+ Protein); t_4 is an indicator variable for time at 4 months post baseline testing; $X t_4$ is an interaction term for treatment and time; and b_1 through b_3 are empirically derived regression coefficients. An unstructured covariance matrix, an identity link function, and robust standard errors will be used. The effect of intervention on each mechanistic factor will be assessed by estimating the magnitude of the coefficient b_3 , which is interpreted as mean change in outcome from baseline to 4 months comparing PUSH Plus Protein to PUSH alone. The primary outcome will be the 6-minute walk test (6MWT). Other potential outcomes include: activities of daily living (ADLs), quality of life, lower-extremity physical performance, increase of ≥ 50 meters in distance walked in six minutes, cognitive status, and nutritional status.

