15.1 Data Management

15.1.1 Processing of Paper Data Forms

Field staff will bring in data forms within 1 week of the visit and place them in the appropriate tray in the study office. Office staff will review each form for completeness and check any required fields. Submitted data forms will be tracked in an Access® database. Forms are then double entered into the appropriate data entry database and filed in the participant binder.

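### The all-items rule in Section 14.3 leaves a participant with 18 of 19 ADL answers without a score, unless a published rule is shown to cover the modified PAT-D

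*Protocol*

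**What the plan says.** Protocol Section 14.3 and the SAP section on missing data carry the same text. One group of scales at the 16-week assessment is exempted: "scores for scales that have published rules for handling missing scale items (e.g., the CES-D and the SF-36) will be calculated using those rules". The next sentence covers the rest: "All other scales will be considered missing if any part of the scale is missing". Scores that are then missing go to inverse-probability weighting: "To correct for potential selection bias from missing data, we will perform a weighted estimating equations (WEE) analysis".

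The ADL measure is described in Protocol Section 9.3.3. Two items were added to the PAT-D, and "two items (walking several blocks and lifting heavy objects) were deleted to avoid duplication with other items in the scale". The section continues: "The resulting 19-item scale allows examination of three subscales (basic ADL, functional limitations, and instrumental ADL"). The number of items per subscale is not given. Section 14.2 places the measure among the non-primary outcomes: "Other potential outcomes include: activities of daily living (ADLs), quality of life, lower-extremity physical performance".

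Two other statements bear on how often items will be missing. The opening of Section 9 says: "All of the measures will be interview-based or based on observations of performance or physiological assessments". Section 15.1.1 says: "Office staff will review each form for completeness and check any required fields".

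**The concern.** A long scale scored only when every item is present is fragile, because each item is a separate chance to lose the whole score. On the plain reading, a participant who answers 18 of 19 ADL items is treated like one who answered none. Weighting then lets other participants stand in for that person, although most of the person's own answers are on the form.

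The exception for published rules does not clearly rescue the PAT-D. A rule written for the original instrument does not automatically carry over to a version with two items added and two removed, and neither document names a rule for it. The paragraph also seems not to have been fitted to this study's instruments: one of its two example scales, the CES-D, is not in the assessment lists of Sections 10.1 and 10.2.

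At stake are precision in a pilot group of about 27 and comparability with CAP. The documents do not say how CAP handled missing ADL items. If the two sources were scored by different rules, the group-by-time coefficient would partly reflect scoring.

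**Working it through.** **Inputs from the documents.** 19 items (Section 9.3.3). Effective n of 94 (CAP PUSH) and 27 (pilot) after 10% attrition, within-subject correlation 0.70, two-sided alpha 0.05, 80% power, detectable difference 0.475 SD (Section 14.4 and SAP).

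**Assumed, because the documents are silent.** Item non-response p of 0.5%, 1% and 2%; about 6 items per subscale; intra-person correlation (ICC) of missingness of 0 (independence), 0.1 or 0.4.

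**Step 1: the plan's own figure.** The SD of change is SD × √(2(1 − 0.70)) = 0.7746 SD. The detectable difference is (1.960 + 0.842) × 0.7746 × √(1/94 + 1/27) = 0.474 SD, which agrees with the stated 0.475.

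**Step 2: share of scores lost under the all-items rule.** With k independent items the loss is 1 − (1 − p)^k. With clustering I use a beta-binomial with a = p(1 − ICC)/ICC and b = (1 − p)(1 − ICC)/ICC; the loss is then 1 − Π (b + j)/(a + b + j) over j = 0 to k − 1.

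| Setting | p = 0.5% | p = 1% | p = 2% |
|---|---|---|---|
| 19 items, independent | 9.1% | 17.4% | 31.9% |
| 19 items, ICC 0.1 | 5.2% | 10.1% | 19.2% |
| 19 items, ICC 0.4 | 2.2% | 4.4% | 8.5% |
| One 6-item subscale, independent | 3.0% | 5.9% | 11.4% |

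At p = 0.1% with independence, the 19-item loss is 1.9%.

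**Step 3: effect on n and precision, independent case, rule applied to both groups.** 27 × (1 − loss) = 24.5, 22.3 and 18.4. 94 × (1 − loss) = 85.5, 77.7 and 64.0. Putting these into the Step 1 formula raises the detectable difference from 0.474 to 0.497, 0.521 and 0.574 SD, and power at 0.475 SD falls from 80% to 76%, 72% and 64%. The plan quotes 0.41 SD for other CAP measures without stating its assumptions, so the relative change is the safer figure: 1/√(1 − 0.091) = 1.05 and 1/√(1 − 0.319) = 1.21, or 5% to 21% larger. At ICC 0.4 it is 1/√(1 − 0.022) = 1.01 to 1/√(1 − 0.085) = 1.05.

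**Step 4: the half-items rule.** A 6-item subscale is lost only if 4 or more items are missing. With independence, that binomial tail is 9.3 × 10⁻⁹ at p = 0.5% and 2.3 × 10⁻⁶ at p = 2%. At ICC 0.4 the beta-binomial tail is 0.2%, 0.5% and 1.0%. Applied to all 19 items at once (lost if 10 or more are missing), it is 0.3%, 0.6% and 1.2% at ICC 0.4. Clustering therefore narrows the gap between the two rules from both sides, but the half-items rule keeps more scores in every setting tried.

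**The case against.** The strongest reply is that the rule may not reach the PAT-D at all. The list of scales with published rules is open, Section 9.3.3 says that adding the two items matches the version used in another cited study, and scoring for a close variant may exist. This stands as a condition on the point. It does not settle the matter, because the plan names no rule and two items were also removed.

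Second, data come from interviews or observation and forms are checked for completeness, so non-response may be low. That is fair, and it favours the lower part of the range. It does not exclude refusals or tasks the participant no longer does, and Section 15.1.1 describes no re-contact for missing items.

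Third, weighting is already planned. It addresses selection bias if the missingness model is right, but it does not use the discarded answers or restore their precision.

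Fourth, averaging answered items has its own bias. If the hard tasks are the ones skipped, the mean of the easier items also leans toward better function. This stands: the change recovers data, but it does not cure that bias.

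A reader might also infer that one missing instrumental-ADL item discards the other two subscales. Section 14.3 does not say whether a scale means the total or a subscale, and Section 9.3.3 allows subscales to be examined, so the text does not establish this.

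**Conclusion.** The point holds conditionally and is a cheap improvement to a non-primary analysis. Unless a published rule is shown to apply to the modified PAT-D, the plan discards nearly complete ADL questionnaires. The size rests on assumptions: 9% to 32% of total scores at 0.5% to 2% independent item non-response, about 2% to 9% at the same rates with ICC 0.4, and about 3% to 11% per subscale with separate scoring of roughly 6 independent items. The primary outcome, walking distance, is not a multi-item scale and is untouched.

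Three stronger readings are not supported. The 9% to 32% is not a forecast for this trial, because the documents give neither a non-response rate nor a reason to assume independence. Bias of the all-items score toward better function is plausible but not shown; its usual rationale, that more disabled people skip several items, implies clustering and so the smaller losses. Nor does the point extend to the MNA-SF: Section 9.3.5 describes a developer-approved modification for interviewer use, with a 0 to 14 score read against fixed cut-offs, and a mean of answered items does not fit that.

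**What to change.** In Section 14.3 and the SAP, add a rule for the modified PAT-D. Score each subscale separately as the mean of its answered items when at least half are answered, and set that subscale to missing otherwise. Apply the same rule to the CAP PUSH item data. Report the all-items-complete score as a sensitivity analysis. If the investigators hold that a published rule already covers this version of the scale, the text should name it and say whether it works by total or by subscale. Do not carry the half-items mean over to the MNA-SF.

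The cost is about one sentence in each document plus rescoring of CAP, which needs item-level CAP data; the documents do not say whether these are available. The statistical price is the assumption that a person's unanswered items resemble the answered ones in the same subscale. Reporting how many items are missing, and which, by group would let readers judge that assumption.
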